1 INTRODUCTION

1.1 STUDY RATIONALE AND BACKGROUND

Bronchiolitis is the leading cause of hospitalization in infants and the fourth leading cause of hospitalization overall in children.¹ The condition is self-limited with few therapeutic interventions demonstrating meaningful benefit.² As such, hospitalization generally consists of supportive care with hydration, oxygen, and other forms of respiratory support as needed.

Given the current unsustainable pace of US healthcare spending, close examination of costly but unproven practices is essential.³ Because of the high prevalence of bronchiolitis and the abundant evidence of overuse of unnecessary tests and treatments,⁴⁻⁸ bronchiolitis care has been the focus of numerous recent high-value care improvement efforts.^{5,6,8-11} However, none of these efforts have addressed routine outpatient follow-up after hospital discharge, a common but understudied intervention.

While routine follow-up after hospitalization is often recommended, regardless of the condition, the benefits, harms, and overall value of this core component of healthcare delivery are only just starting to be evaluated critically.¹²⁻¹⁴ Potential benefits include increasing parental reassurance, strengthening the relationship between a family and the child's primary care provider (PCP), and modifying treatment to speed disease resolution or prevent disease exacerbation. On the other hand, routine follow up visits cost money, may be burdensome for families, and may precipitate additional, unnecessary medical care. For example, a recent randomized trial involving 1,500 patients discharged from Cincinnati Children's Hospital demonstrated that the intervention (a nurse-led home visit after discharge) was unexpectedly associated with an increased risk of acute healthcare reutilization (including readmission and emergency department visits) compared with no home visit.¹⁵ Overdiagnosis (the detection of conditions where such detection does not benefit patients¹⁶) may be one explanation for these findings. In other words, exposure to a medical encounter may uncover abnormalities that otherwise would have gone undetected and not caused harm had such a visit not occurred. In bronchiolitis particularly, overdiagnosis of hypoxemia detected by routine pulse oximetry is a well-described phenomenon.^{7,17-20}

Our study will assess the relative benefits, risks, and costs of two different follow up strategies for children with bronchiolitis who are discharged from the hospital. Our findings will impact management of over 100,000 hospitalizations per year nationally.²¹ Furthermore, results from this study can be used to inform follow up practices for other common, self-limited pediatric conditions.

1.2 PILOT DATA

To prepare for BeneFIT, we conducted an observational pilot study²² of children hospitalized for bronchiolitis during the winter of 2016-17. All five BeneFIT medical centers (listed in section 3) participated. Among 199 enrolled subjects, a routine follow-up visit was either recommended or scheduled by the primary team in 84% of cases. Two-thirds of patients who completed the study attended a routine follow-up visit, including 87% of those who had a follow up appointment scheduled prior to hospital discharge and 33% of those for whom as needed follow up was recommended.

"Reassurance provided" (70%) and "education provided" (15%) were cited by parents as the most useful aspect of the follow-up visit. Hospital re-visits were uncommon (2%).

2 OBJECTIVES AND ENDPOINTS

2.1 PRIMARY OBJECTIVE AND ENDPOINT

The primary objective of the study is to determine whether as needed Primary Care Physician (PCP) follow-up is non-inferior to scheduled PCP follow-up in terms of reduction in parental anxiety.

Primary Outcome

Parental anxiety, as measured by the anxiety portion of the Hospital Anxiety and Depression Scale (HADS),²³ a validated tool used in a previous trial among parents whose children had been hospitalized for bronchiolitis.¹⁹ Parental anxiety will be measured by research coordinators at before hospital discharge (baseline) and at the first data collection phone call (5-9 days following discharge). The same parent will be interviewed for both the baseline and the follow up HADS. If the length of time between baseline HADS and actual discharge exceeds 2 days, the HADS will be repeated, such that each subject has a baseline HADS within 2 days of hospital discharge.

Justification of Primary Outcome

Our primary outcome was selected based on feedback from primary care providers and parents of children hospitalized for bronchiolitis. Among parents surveyed in our pilot study, "reassurance" was most commonly selected (70%) as the most valuable aspect of the follow up visit.²² Parental reassurance was also mentioned repeatedly by primary care providers from Stanford, Intermountain, and elsewhere via informal discussions with the investigators.

2.2 SECONDARY OBJECTIVES AND ENDPOINTS

Secondary objectives of the study include determining whether as needed PCP follow-up, compared to scheduled PCP follow-up:

- Does not adversely impact satisfaction with care?
- Does not adversely impact the relationship between the child's primary caregiver and the child's PCP?
- Does not prolong time to resolution of symptoms?
- Does not increase risk of hospital re-admissions and emergency department visits?
- Results in a fewer number of post-discharge ambulatory visits?
- Results in less ambulatory testing (pulse oximetry, chest x-ray) and fewer prescriptions (albuterol, antibiotics, steroids)?
- Results in fewer missed days from daycare and work?
- Results in lower medical costs?

Secondary Outcomes

Measured by parent report via weekly research coordinator phone calls, until symptoms resolved or 50 days after discharge, whichever occurs first:

- Time from hospital discharge to cough resolution
- Time from hospital discharge to child reported back to normal

Measured by parent report via weekly research coordinator phone calls, until symptoms resolved or 50 days after discharge, whichever occurs first:

- Number of hospital re-admissions and emergency visits
- Number of ambulatory visits
- Number of missed daycare and work days
- Ambulatory prescriptions (albuterol, antibiotics, steroids)
- Ambulatory testing (i.e. pulse oximetry, chest x-ray)- only measured at first ambulatory visit

Measured by parent report via research coordinator phone call at 1 month from discharge:

- Relationship with PCP measured by the Patient-Doctor Depth-of-Relationship Scale²⁴
- Satisfaction with care, measured by applicable questions from the Patient Satisfaction Questionnaire Short Form (PSQ-18)²⁵
- Immunizations received

Measured among patients cared for at Intermountain clinics and those who have Select Health insurance:

- Total charges for ambulatory medical care from discharge until:
 - 14 days after discharge
 - symptom resolution

Measured at the time of discharge and during the first follow up phone call:

• Perceptions about pulse oximetry monitoring

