6.2 STUDY PROCEDURES

Consent, screening and study enrollment will occur while the participant is hospitalized for bronchiolitis. Eligibility confirmation will be obtained from the electronic medical record along with parent interview as applicable. Prior to randomizing the eligible patient, the child's parent will be asked to complete the anxiety portion of the HADS, administered verbally by research coordinators. When a RedCap enrollment checklist has been completed, RedCap will supply the local research coordinator with the patient's randomization assignment. The parents will be notified of their randomization group and instructed on the study plan for follow-up as discussed in section 6.1. Patients discharged home with supplemental oxygen will not be randomized, with follow up plans determined by the child's medical team.

Prior to hospital discharge, a research coordinator will call the child's PCP to notify them of the child's enrollment in the trial and their randomization assignment. The research coordinator will fax a one page summary of the trial to the PCP. PCPs will be notified at the time of the call and in the one-page summary that the protocol allows for and encourages PCPs to check-in over the phone with families enrolled in the trial.

Demographic and hospitalization details will be obtained via electronic medical record review. Data for the primary endpoint will be collected by administering the anxiety portion of the HADS survey prior to randomization and at the first post discharge follow-up phone call (5-9 days after discharge). Data for the secondary endpoints will be collected via phone calls from a research coordinator and will occur weekly until symptom resolution or 50 days after discharge, whichever comes first. Research

coordinators will follow a script for all data collection phone calls. Electronic medical record review will supplement information collected by phone calls for patients who re-visit the emergency department or are re-admitted to the hospital. In addition, a one month post discharge phone call will be made to administer the Patient-Doctor Depth-of-Relationship Scale questionnaire. Study participation will conclude with the final discharge phone follow up call.

Table 1: Schema of study procedures

Screening/Enrollment Within 2 days of anticipated hospital discharge

- •Screen potential participants by inclusion and exclusion criteria
- •Obtain informed consent and enroll

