- •Obtain demographics and relevant medical history
- •After consent and eligibility verification, but before randomization, parent or legal guardian will complete anxiety portion of HADS

Randomization Day of discharge (patients discharged on oxygen will not be randomized)

- •Coordinator will obtain patient randomization assignment
- •Coordinator will notify child's PCP of child's enrollment in study and randomization assignment
- •Scheduled follow up: Family instructed to follow-up with PCP (appointment made prior to discharge)
- •As needed follow up: Family will be instructed to follow-up with PCP on as needed basis

7 day phone call F	Follow-up assessments of study endpoints
--------------------	--

• Parent will complete anxiety portion of the Hospital Anxiety and Deptression Scale (HADS)

• Parent assessment for secondary outcomes collected via phone interview (see script)

Subsequent weekly phone calls Follow-up assessment of study endpoints

• Parent will be contacted weekly to collect secondary endpoint data until symptom resolution or 50 days after discharge whichever comes first (see script)

1 month follow-up

Follow-up Telephone Call

• Patient-Doctor Depth-of-Relationship Scale will be administered

• Participant considered off study at this timepoint or when final weekly phone call occurs (if needed beyond 4 weeks)

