6.3 MEASURES TO MINIMIZE BIAS: RANDOMIZATION AND BLINDING

Randomization

After consent and enrollment, a research coordinator at the site will obtain a site-specific computergenerated randomization assignment for each patient. Patients will be randomized with equal (1:1) allocation to either the scheduled PCP follow up group or to the as-needed PCP follow up group, using randomly permuted blocks of random sizes. Randomization sequences will be stratified by site but not by any additional baseline factors. The research coordinator will inform the patient's family, inpatient medical team, and PCP of the patient's assignment.

Blinding

BeneFIT will be an unblinded trial because it will not be feasible to blind parents or research coordinators to intervention assignment, as the reason for any follow-up visit (i.e. routine vs new concern) that occurs needs to be documented. However, investigators responsible for analyses will be blinded to individual patient intervention assignments.

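### Re-admission, ED-visit and other utilization counts stop at parent-reported symptom resolution, so there is no common observation window; the resulting loss is unknown and may be near zero

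*Combined protocol and SAP*

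**What the plan says.** Section 2.2 lists the numbers of re-admissions and emergency visits, ambulatory visits, missed daycare and work days, and ambulatory prescriptions under this rule: "Measured by parent report via weekly research coordinator phone calls, until symptoms resolved or 50 days after discharge, whichever occurs first". Table 1 in Section 6.2 repeats it: "Parent will be contacted weekly to collect secondary endpoint data until symptom resolution or 50 days after discharge whichever comes first". The related objective in Section 2.2 has no time limit: "Does not increase risk of hospital re-admissions and emergency department visits".

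Three other provisions bear on the point.

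- **Record review (Section 6.2):** "Electronic medical record review will supplement information collected by phone calls for patients who re-visit the emergency department" or are re-admitted. No window is given, and no search of all participants is stated.
- **1-month call (Section 6.2):** "In addition, a one month post discharge phone call will be made to administer the Patient-Doctor Depth-of-Relationship Scale questionnaire". Section 2.2 adds satisfaction and immunizations at that time. No utilization items are listed.
- **Charges (Section 2.2):** these have both a fixed 14-day window and an until-resolution window, in a subset of patients. The counts have no fixed window.

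Section 7.2.1 compares the counts by Poisson or negative binomial regression and mentions no offset, exposure time or common period. Its censoring rule (day 50 or loss to follow-up) applies only to time to symptom resolution. Section 6.3 states that "it will not be feasible to blind parents or research coordinators to intervention assignment".

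**The concern.** A child reported well at the first call (day 5 to 9) may contribute about a week of observation, while another contributes 50 days. The length of observation is determined after randomization, is reported by parents who know the assignment, and is itself a secondary outcome compared between arms. The stopping point is also not uniquely defined: Section 2.2 treats cough resolution and return to normal as separate outcomes and does not say which one ends the calls.

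The re-visit objective reads as a safety question about the period after discharge, but the data cover only the time to reported resolution. If resolution and its reporting are the same in both arms, the result is undercounting without bias. If either differs by arm, a comparison meant to cover a fixed period is mixed with a difference in window length. With few re-visits expected, one or two missed events would be a visible share of the total.

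**Working it through.** **Plan's own figure.** The only sample size stated is for the primary outcome. Residual SD = 4.1 × √(1 − 0.65²) = 3.116 and margin = 2 × (1 − 0.33 − 0.13) = 1.08. With one-sided α = 0.025 and 80% power, the normal approximation gives 131 evaluable per arm; 131/0.9 rounds up to 146, or 292 in total. The noncentral t gives 132 evaluable; 132/0.9 rounds up to 147, or 294 in total. The plan's 294 reproduces, and this concern does not touch it.

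**Expected re-visits.** At the pilot rate of 2% (Section 1.2), 147 × 0.02 = 2.94 per arm.

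**Share of 30-day events missed.** The documents give neither time to resolution nor event timing, so every input here is an assumption:

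- time to resolution T is exponential with mean m = 7, 10, 14 or 20 days;
- the window W closes at the next multiple of 7 days at or after T, or at day 50 if T > 49;
- event intensity at day t is proportional to exp(−t/d), with d = 5, 7 or 10 days, multiplied by 1 before T and by r after T.

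Capture = expected events before min(W, 30) ÷ expected events before day 30. The share missed is 1 − capture.

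| r (rate after vs before resolution) | Capture, all m and d | Missed | Capture at m = 14 (d = 5 / 7 / 10) | Missed at m = 14 |
|---|---|---|---|---|
| 0 | 1.000 | 0% | 1.000 | 0% |
| 0.25 | 0.847–0.975 | 2.5–15.3% | 0.965 / 0.942 / 0.913 | 3.5–8.7% |
| 0.5 | 0.754–0.952 | 4.8–24.6% | 0.935 / 0.895 / 0.847 | 6.5–15.3% |
| 1 | 0.648–0.914 | 8.6–35.2% | 0.888 / 0.824 / 0.753 | 11.2–24.7% |

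An extreme case (r = 1, constant rate, m = 14) has capture 0.522, so 48% missed.

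**In events per arm.** If the pilot 2% is a complete 30-day rate, the number missed is 2.94 × (1 − capture): 0 at capture 1.00, 0.29 at 0.90, 1.03 at 0.65 and 1.41 at 0.522. If the pilot figure was itself collected only until resolution, 2.94 is already the captured number and nothing should be subtracted.

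**Power of the re-visit comparison.** The test is two-sided Fisher exact at 0.05, counting rejections in the direction of harm, with 132 per arm (90% of 147). The assumed 2% versus 6% are each multiplied by capture. Power is 26% at full capture, 24% at 0.95, 22% at 0.90 and 13% at 0.65.

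**Reporting difference alone.** Suppose the illness is identical in both arms, but 20% of families in one arm report resolution one call later (W + 7, capped at 50). Over m = 7, 14, 20 and d = 5, 7, 10, the ratio of expected counts is 1.00 at r = 0, 1.004–1.021 at r = 0.25, 1.008–1.038 at r = 0.5 and 1.015–1.063 at r = 1.

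**The case against.** The strongest reply is that the plan does state a window: until resolution or day 50 is the definition of the outcome. Counting over the illness episode is a legitimate estimand, and the two windows given for charges suggest the choice was deliberate. The same stopping rule applies to both randomized arms. This stands in part. The plan never names an episode-based estimand, however, and the re-visit objective is not limited to the symptomatic period.

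Second, the consequence may be small. The loss is zero if re-visits occur only while symptomatic, and it depends on the assumed shape of resolution. A gamma distribution (shape 3, mean 14 days) has 19% of children resolved by day 7 against 39% for the exponential. It lowers the loss to 2–6% at r = 0.25, 4–11% at r = 0.5 and 7–19% at r = 1. Power for re-visits is low even at full capture. All of this stands and limits the weight of the point.

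Third, non-capture is not proven. Section 6.2 says that "coordinators will follow a script for all data collection phone calls", but the script is not in the text and could ask about re-visits at one month. The record review has no stated end date. Everyone reached is observed to at least day 5 to 9, after the scheduled visit is due (within 4 days). These are fair points, but an unstated provision does not define a window, and the record review does not cover ambulatory visits, missed days or prescriptions.

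Finally, events unrelated to the episode could dilute a comparison intended to show no increase. That is a reason to keep the episode-based counts alongside the fixed-window counts. It does not justify leaving the period undefined.

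**Conclusion.** The concern holds. The observation period for these counts is itself a post-randomization outcome, and no stated provision clearly captures events after reported resolution. The size of the loss is unknown. Across the assumptions used it runs from 0% to 35% of 30-day events (48% in the constant-rate extreme), or 0 to 1.0 re-visits per arm (1.4 in the extreme) if the pilot 2% is a complete 30-day rate. The documents do not show that resolution or reporting will differ by arm, so bias is possible but not established. A modest reporting difference alone moves the count ratio by at most about 6% under these assumptions.

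The change should be made but is not critical. These are secondary outcomes, the re-visit comparison is weak at any level of capture, and the primary analysis is unaffected. What is gained is a re-visit count that refers to a defined period for every child.

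**What to change.** - Define re-admissions and ED visits, and the other call-collected counts, over one fixed window from discharge (for example days 0 to 30) for every randomized child.
- Make the existing 1-month call on or after the last day of that window. Ask every family about these events since their last call, whatever the symptom status.
- Apply the record review for ED visits and re-admissions to all randomized children over the same window.
- In Section 7.2.1, use an exposure offset only for loss to follow-up. An offset for time to resolution would condition on a post-randomization outcome and would not recover later events.
- Keep the until-resolution counts (to day 50) as a supplementary analysis, named as episode-based, and state which symptom outcome ends the episode.

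The cost is a few questions on a call already planned, a record check for up to 294 children, and some SAP wording. The main drawback is recall: a family whose calls ended at day 5 to 9 would be asked at day 30 about the previous 21 to 25 days. Record review helps with this for ED visits and re-admissions but not for missed days.

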6 STUDY ASSESSMENTS AND PROCEDURES

6.1 STUDY INTERVENTION

Scheduled follow up

At the time of hospital discharge, parents will be instructed to have their child follow up with their PCP within 4 days of discharge regardless of improvement and/or symptom resolution. Research coordinators will verify that the child has a scheduled follow up appointment prior to discharge and will help with scheduling if necessary.

As needed follow up

At the time of hospital discharge, parents will be instructed that the child does not need to automatically follow up with his/her primary care physician. Rather, the child should follow up on an as needed basis: if the child does not improve or if new concerns arise.

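### The objective is less ambulatory testing, but tests are recorded only at the first ambulatory visit, so the outcome cannot answer the objective as stated

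*Combined protocol and SAP*

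**What the plan says.** Section 2.2 of the combined protocol and SAP lists among its secondary objectives whether as-needed follow-up "Results in less ambulatory testing (pulse oximetry, chest x-ray) and fewer prescriptions (albuterol, antibiotics, steroids"). The objective has no limit to one visit. The outcome that serves it does: "Ambulatory testing (i.e. pulse oximetry, chest x-ray)- only measured at first ambulatory visit". Ambulatory visits and prescriptions stand under the same heading, are collected in the same weekly calls until symptoms resolve or day 50, and carry no such limit.

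Charges are also collected ("Total charges for ambulatory medical care from discharge until" day 14 or symptom resolution), but only in a subset: "Measured among patients cared for at Intermountain clinics and those who have Select Health insurance".

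Section 6.1 tells scheduled-arm families to "follow up with their PCP within 4 days of discharge regardless of improvement and/or symptom resolution". As-needed families are told to come back only if the child fails to improve or something new worries them. Section 7.2.1 places testing among the other secondary outcomes, compared between randomised groups with Poisson or negative binomial models. It mentions neither the first-visit limit nor how a child with no visit is counted.

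**The concern.** The objective is about total testing after discharge, and the outcome sees one visit. Section 1.1 motivates the trial partly by the possibility that "routine follow up visits cost money, may be burdensome for families, and may precipitate additional, unnecessary medical care", and it singles out overdiagnosis of hypoxemia by oximetry. A test that follows from the routine visit but is done at a later visit is part of that question, and first-visit data cannot show it.

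Assignment also changes what kind of visit comes first. In the pilot (Section 1.2), a routine visit was attended by "87% of those who had a follow up appointment scheduled prior to hospital discharge" and by "33% of those for whom as needed follow up was recommended". If later visits carry tests, the fraction left unrecorded need not be the same in the two arms. What is at stake is a secondary conclusion: a first-visit result could be reported as less, or no less, testing overall.

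**Working it through.** **1. The plan's own figures.** The documents give no figure for ambulatory testing. The one design figure is the sample size in Section 7.1. The residual SD is 4.1 × √(1 − 0.65²) = 3.116. With margin 1.08, one-sided α 0.025 and 80% power, this needs 131 per arm. Dividing by 0.90 gives 146 per arm, or 292 in total against the stated 294. None of these inputs concerns testing, so the point does not touch N.

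**2. Objective against outcome (no assumption needed).** Objective: all ambulatory testing. Outcome: first visit only. No section narrows the objective or gives a reason for the limit.

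**3. Illustration of the share missed.** From the documents: routine attendance a = 0.87 (scheduled) and 0.33 (as needed). Assumed, because the documents are silent: oximetry at 50% of routine visits (pr) and 80% of concern visits (pc); a concern-visit rate c that is equal in both arms and independent of the routine visit; the routine visit comes first; no repeat concern visits.

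- True tests per child = a·pr + c·pc
- Recorded tests per child = a·pr + (1 − a)·c·pc
- Share missed = 1 − recorded/true

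At c = 20%:
- Scheduled: true 0.435 + 0.160 = 0.595; recorded 0.435 + 0.13 × 0.160 = 0.456; missed 23%.
- As needed: true 0.165 + 0.160 = 0.325; recorded 0.165 + 0.67 × 0.160 = 0.272; missed 16%.

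| c | Share of all tests missed, scheduled vs as needed | As-needed/scheduled ratio, true | Ratio, recorded |
|---|---|---|---|
| 10% | 14% vs 11% | 0.48 | 0.49 |
| 20% | 23% vs 16% | 0.55 | 0.60 |
| 33% | 33% vs 20% | 0.61 | 0.73 |

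The true difference is 0.54 × 0.50 = 27 tests per 100 children in every row. The fraction of it not recorded is c·pc/pr = 16%, 32% and 53%.

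**4. Which visit is first.** Routine share of first visits = a/(a + (1 − a)·c). For c = 10%, 20% and 33% this is 99%, 97% and 95% in the scheduled arm and 83%, 71% and 60% in the as-needed arm. The mix differs, but first visits are mostly routine in both arms.

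**5. Other visit patterns.**
- Concern visits only in children without a routine visit, none repeated: every test falls at a first visit, and the bias is zero.
- The same, but half of those children return once (c = 20%): scheduled true 0.435 + 0.13 × 0.20 × 1.5 × 0.80 = 0.466; as needed true 0.165 + 0.67 × 0.20 × 1.5 × 0.80 = 0.326. The true ratio is 0.70 and the recorded ratio 0.60, so the error now favours as-needed follow-up.
- Equal testing probability at every visit and a Poisson number of other visits with mean 0.25 in both arms: 20% vs 18% missed, ratio 0.52 true and 0.53 recorded, so almost no distortion.

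**6. Can the sign change?** Under step 3, the recorded difference (as needed minus scheduled) is −0.54 × (pr − c·pc). It changes sign only if c·pc exceeds pr, that is, for a test that is uncommon at routine visits. With assumed chest x-ray rates of 2% and 20% and c = 20%, the ratio is 0.81 true and 1.48 recorded. Expected counts per 147 are only about 8 vs 7 true and 3 vs 5 recorded, and the recorded ratio has a 95% interval of about 0.4 to 6.0. That supports no conclusion under either definition.

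**The case against.** The limit is stated openly, in the same section as the objective, so a careful reader knows what will be reported. On the natural reading of the intention-to-treat heading in Section 7.2.1, first-visit testing is counted over all randomised children and is a valid randomised comparison. Later care is partly visible in visit counts, prescriptions, emergency visits and re-admissions. In the simplest visit pattern the distortion is negligible. Recording one visit may also spare families and limit recall error.

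Most of this stands, and it limits the point. It does not close the gap, because visits and prescriptions do not count tests, and charges are totals in a subset. The documents do not give burden or recall as a reason, and the same families are already asked about visits and prescriptions each week.

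Three stronger readings are tempting and not supported:
- A reader might infer that 87% vs 33% of tests go unrecorded. Those figures are the pilot attendance rates. Under the assumptions of step 3 they apply to concern-visit tests only. For all oximetry tests the figures are those in the table.
- A reader might infer that the outcome understates the saving from as-needed follow-up. That holds under one visit pattern; others give zero or the opposite.
- A reader might infer that the result will point the wrong way. That needs rates the documents do not contain. Under the assumed oximetry rates the direction is unchanged, and for x-ray the expected counts are too few.

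**Conclusion.** The mismatch is in the text and needs no assumption: as written, the trial can report testing at first ambulatory visits but cannot say whether as-needed follow-up leads to less ambulatory testing. That the share missed could differ by arm is a possibility that follows from the two follow-up instructions. It is not a demonstrated bias. Its size and direction depend on testing rates, concern-visit rates, visit order and repeat visits, none of which the documents give. Only the 87% and 33% attendance figures come from the text, and they are observational pilot data. The matter should be corrected because the correction is cheap. It affects one secondary outcome and leaves the primary analysis untouched.

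**What to change.** Define the outcome as pulse oximetry and chest x-ray at any ambulatory visit until symptom resolution or day 50, the window already used for visits and prescriptions. In the scripted weekly calls, ask about both tests for each visit reported since the last call. Analyse tests per randomised child with the Poisson or negative binomial model already planned, and state that a child with no visit counts as zero. Keep first-visit testing as a descriptive table by visit reason (routine or new concern), which Section 6.3 already requires to be documented.

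Cost: no additional calls, but slightly longer ones for families with more than one visit. The call script is not in the documents, so the added length is an assumption: two questions per later visit. Under the assumptions of step 3, the number of families affected is 147 × (0.87 + 0.33) × c, or about 18, 35 or 58 of 294 at c = 10%, 20% or 33%.

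If this is not feasible, restrict the objective and its conclusion to testing at the first ambulatory visit, and state that total testing is not assessed. That costs only a wording change.
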